Multiple studies have been performed in the past assessing local infiltration of multiple different kinds of anesthetic and pain medications either before cesarean delivery begins or at the end of the procedure for pain control.^{7,8,17-19,9-16} These studies have had conflicting results on the utility of local anesthetics for postoperative pain control. A Cochrane review from 2009 noted that local infiltration was likely beneficial in reducing postoperative opioid consumption but not visual analog pain scales.²⁰ A metanalysis published in 2017 also noted that local infiltration was likely beneficial in reducing postoperative opioid consumption but its utility when used in combination with intrathecal opioids in spinal regimens (as is now the standard of care in obstetrical anesthesia) required more data.²¹

The most recently published randomized controlled trial on this topic is from Egypt in 2016 assessing postoperative pain with local infiltration of lidocaine versus lidocaine with epinephrine in women undergoing general anesthesia.²² This study demonstrated safety of both regimens and showed improved pain relief for women receiving lidocaine with epinephrine. Our study seeks to assess pain relief with incisional infiltration of local anesthetic (with and without epinephrine) during cesareans performed under spinal anesthesia also using intrathecal opioids. Our study is more relevant given the infrequency of cesareans performed under general anesthesia in the United States. We will also be assessing women who receive no local infiltration of anesthetic, the current standard of care, as our control group.

Multiple professional societies and government agencies have recommended a decrease in the use of opioids for postoperative analgesia given the opioid misuse epidemic. Our study attempts to further assess postoperative oral opioid consumption in patients undergoing spinal anesthesia with intrathecal opioids by assessing the addition of local subcutaneous infiltration of anesthetic.

Study Design

Objective: The objective of our study is to assess the addition of subcutaneous bupivacaine (Marcaine) with or without epinephrine to the standard intrathecal morphine/fentanyl combination given during spinal anesthesia during elective cesarean delivery on postoperative pain control as measured by postoperative usage of oral opioids and a postoperative pain assessment scale.

Hypothesis: The addition of subcutaneous bupivacaine with epinephrine at the cesarean incision site prior to skin closure to the standard spinal anesthesia regimen at the time of elective cesarean delivery will reduce postoperative narcotic usage in the first 24 hours postoperatively by 25%

Null Hypothesis: There will be no difference in postoperative narcotic usage in the first 24 hours after cesarean delivery with the addition of subcutaneous bupivacaine with or without epinephrine at the cesarean incision site prior to skin closure at the time of elective cesarean delivery.

Methods: Trial will be registered on ClinicalTrials.gov and follow CONSORT guidelines

- Type of study: 3 arm, blinded, randomized controlled trial involving patients who receive spinal anesthesia for elective cesarean delivery
 - *Randomization:* Subjects will be randomized using the blocking method. To achieve comparable groups, we will randomize enrollees to one of three treatment arms. Randomization will be done with block sizes of 6 to reduce the likelihood of unmasking the randomized assignment. All potential subjects will be randomized prior to study start (patient's # 001- 276) and the group that they are randomly assigned to will be written on cards placed into pre-sealed envelopes.
 - *Blinding:* The envelopes will not be opened, and the subjects' group not known, until immediately prior to the subjects' cesarean delivery to maintain the randomization process. Only the physicians drawing up and supplying the medication (the anesthesia physicians- resident and attending) will be aware of the patients group. The physicians administering the medication (i.e. the OBGYN attending and resident) will NOT be told the composition of what they are injecting. The patient will be blinded to (i.e. will not be told) their intervention group. The investigator collecting the data will be blinded to (i.e. not know) which intervention group each individual patient was assigned to while collecting the data. Therefore, the patient, the physician administering the medication, and the personnel collecting the data will all be blinded to the patient's intervention group. The anesthesia team will only record the patient's pre-assigned number into the medical record (EPIC electronic

 - cumulative usage of postoperative pain medication- opioid (oxycodone) (at 4 hours, 8 hours, 12 hours, 24 hours, 36 hours, 48 hours postoperatively)
 - Time to first postoperative pain medication
 - Need for additional breakthrough pain medication outside of protocol (amount and type of medication will be documented)
 - Subjective patient pain assessment
 - immediate postoperative pain scale performed in postoperative anesthesia care unit (PACU) and throughout the postoperative period according to current nursing protocol (see above)
 - Patient satisfaction with pain management
 - Time to return of bowel function
 - Time to discharge from the recovery room
 - Time to first ambulation
 - Breastfeeding during hospital stay (assessment of both initiation of and exclusive breastfeeding)
 - Maternal side effects/outcomes
 - Intraoperative: hypotension, nausea, vomiting, pruritus, respiratory depression, prolonged numbness or immobility, failed neuraxial anesthesia requiring intubation, systemic toxicity of local anesthesia
 - Postoperative: fever, postoperative wound separation, postoperative wound infection, skin site irritation, incisional hematoma/seroma formation
 - Other *variables* to be collected:
 - Demographic
 - Maternal: Age, gravidity, parity, number of prior cesarean deliveries, number of prior surgeries, maternal co-morbidities (chronic hypertension, gestational hypertension, preeclampsia, diabetes mellitus -pregestational, gestational-diet or medication controlled- autoimmune disease, known pain syndromes- i.e. fibromyalgia, etc.), reason for current cesarean delivery, history of tobacco use, history of anxiety or depression, amniotic membrane status, body mass index, ethnicity
 - Fetal: gestational age, suspected intrauterine growth restriction, estimated fetal weight, known or suspected congenital or chromosomal anomalies, placenta previa
 - Intraoperative variables

- Length of surgery, estimated blood loss, intraoperative complications, concurrent bilateral tubal ligation, any other analgesia given intraoperatively and amount of other anesthetic given
- Postoperative variables
 - Neonatal outcomes (will be stratified based on fetal gestational age as this study includes all gestational ages and neonatal outcomes will likely be affected by gestational age; we will therefore stratify results by completed weeks of gestation: >37 weeks, 34-37 weeks, 30-34 weeks, <30 weeks)
 - APGARS, APGAR <7 at 5 min, fetal arterial blood gas pH and base deficit, neonatal intensive care unit admission, fetal weight
- **Study Population:** all pregnant female patients who will be undergoing an elective cesarean delivery under spinal anesthesia at any gestational age
 - Inclusion criteria:
 - Elective cesarean delivery with or without planned bilateral tubal ligation
 - Planned spinal anesthesia
 - Planned Pfannenstiel or low transverse skin incision
 - Exclusion criteria:
 - Known maternal allergy to bupivacaine or derivative
 - Known maternal allergy to oxycodone, ibuprofen, acetaminophen or derivative
 - Currently have an epidural catheter in place
 - Planned general anesthesia
 - Maternal age <18 years old
 - Emergent cesarean delivery
 - Active labor [defined as: >6cm cervical dilation and regular contractions noted on tocometer (>2 contractions in a 10 minute period for 30 consecutive minutes)]
 - Chronic antepartum opioid use
 - History of substance abuse (alcohol or drug)
 - Current tobacco use
 - Chronic steroid use or needing stress dose steroids at the time of delivery
 - Medical contraindication to neuraxial anesthesia such as thrombocytopenia (platelet count <80,000/microliter) or space occupying lesion of the brain
 - Category 3 fetal heart rate pattern

- Maternal fever or suspected chorioamnionitis
 - Concern for morbidly adherent placenta
 - Planned cesarean hysterectomy
- **Power analysis:**
 - Sample size was determined assuming a power of 80%, p value of 0.05 to detect a 25% difference in the primary outcome of cumulative opioid usage in the first 24 hours postoperatively
 - In a previous unpublished, randomized controlled study conducted by [name], average use of opioids in post-cesarean subjects was 47mgSD 35 morphine equivalence in the first 24 hours postoperatively
 - Therefore, in our protocol, with three groups and keeping the hypothesis as one of the groups will consume fewer opioids (SD as 25) to demonstrate a minimum 25% difference between any two groups, this will require 255 subjects total (85 subjects per group). However, to accommodate for missing data and study withdrawal we will increase the sample size by 10 % therefore there will be 276 subjects total- or 92 patients per group
- **Exclusion of any population group:**
 - Minors <18 will be excluded
 - There are regulations for protection of human subjects allowing consenting adults to accept a higher level of risk than is permitted for children
 - Only subjects who have the capacity to consent will be enrolled
- **Sources of research material:**
 - Data and access to the electronic medical records (EPIC, EPF, ASOBGYN) will be obtained from individually identifiable living human subjects as part of routine clinical care.
- **Participant recruitment:** Study team members (i.e. key personnel) on labor and delivery will ask patients who present for elective cesarean delivery if they are interested in the study. The key personnel will then approach the intended patients to obtain consent for the research study. We are requesting a waiver of informed consent and HIPAA authorization to access medical records for recruitment purposes.
 - All patients will be told that the study is voluntary, they do not have to participate and whether they participate will not affect their care in any way
 - Maintenance of safety of PHI data/confidentiality
 - All records will be kept in a secure manner on a secure server. Access to the records will only be by the listed protocol key personnel and the computer records will be password protected. All patients will be

assigned a number and all information will be recorded under this number - not patient identifying information - and a separate list will be kept in a separate location under password protection listing medical records of patients identified to the code and only researcher [name] will have access to this list.

- **Informed consent**

- The informed consent document adhering to Montefiore's template is uploaded to IRIS.
- Informed consent will be obtained by listed key personnel when the patients present to the labor and delivery unit. These patients will be approached based on the inclusion/exclusion criteria noted above and will NOT be women in labor as outlined in the exclusion criteria. They are women for elective cesarean delivery.
- There will be no waiver of informed consent and minors will not be included
- There is no cost or remuneration to the participants
- HIPPA authorization will take place at the same time as the informed consent process

- **Risks/Benefits**

- Anticipated risks (e.g. medical, social, psychological, and/or legal)
 - The anticipated medical risks involved with the addition of bupivacaine include possible allergic reaction, systemic toxicity or intravascular injection of the anesthetic. There are no social or legal risks. Psychological risks include discomfort completing questionnaires and breach of confidentiality/ loss of privacy.
 - Risks of injection process include: pain, redness, infection or allergy to medication components
 - Adverse reactions of study medications according to FDA:
 - Oxycodone: abuse, misuse, addiction; (>5%): constipation, nausea, somnolence, dizziness, vomiting, pruritus, dry mouth, sweating, asthenia; (1-5%) anorexia, nervousness, insomnia, fever, confusion, diarrhea, abdominal pain, dyspepsia, rash, anxiety, euphoria, dyspnea, postural hypotension, chills, twitching, gastritis, abnormal dreams, thought abnormalities, hiccups; (<1%): lymphadenopathy, palpitations, tinnitus, syndrome of inappropriate antidiuretic hormone secretion, abnormal vision, dysphagia, flatulence, ileus, stomatitis, increased appetite, eructation, chest pain, edema, facial edema, malaise, pain, peripheral edema, thirst, withdrawal syndrome (with and without seizures), anaphylactic or anaphylactoid reaction, pharyngitis, accidental injury,

hyponatremia, increased hepatic enzymes, ST depression, dehydration, neck pain, abnormal gait, amnesia, hyperkinesia, hypertonia (muscular), hypesthesia, hypotonia, migraine, paresthesia, seizures, speech disorder, stupor, syncope, taste perversion, tremor, vertigo, agitation, depersonalization, depression, emotional lability, hallucination, dysuria, hematuria, polyuria, urinary retention, urination impaired, amenorrhea, decreased libido, impotence, cough increased, voice alteration, dry skin, exfoliative dermatitis, urticarial, vasodilation

- Acetaminophen: (>3%) nausea, vomiting, headache, insomnia, pyrexia; (>1%): anemia, fatigue, infusion site pain, peripheral edema, aspartate aminotransferase increased, breath sounds abnormal, hypokalemia, muscle spasms, trismus, anxiety, dyspnea, hypertension, hypotension
- Ibuprofen: (>1% but <3%) Nausea, stomach pain, heartburn, vomiting, constipation, abdominal cramps, bloating, gas, dizziness, headache, nervousness, rash, itching, ringing in ears, decreased appetite, swelling, fluid retention; (<1%): ulcer, bleeding ulcer, black stools, abnormal liver function tests, inflammation of liver/ pancreas/ stomach, depression, difficulty sleeping, confusion, sleepiness, hives, thinning of hair, Stevens Johnson syndrome, hearing loss, blurred vision or changes in vision, neutropenia, aplastic anemia, thrombocytopenia, eosinophilia, decrease in blood count, elevated blood pressure, bronchospasm, acute kidney failure, blood in urine, kidney injury, increase urination, inflammation of bladder, dry eyes and mouth, gum ulcer, inflammation of nose
- Bupivacaine Hydrochloride: (toxicity most commonly dose related from overdosage, rapid absorption from injection site, diminished tolerance, or from unintentional intravascular injection of local anesthetic) -excitation and/or depression, restlessness, anxiety, dizziness, tinnitus, blurred vision, tremors, convulsions, drowsiness, unconsciousness, respiratory arrest, depression of the myocardium, decreased cardiac output, heartblock, hypotension, bradycardia, ventricular arrhythmias, cardiac arrest, paralysis of legs, loss of consciousness, respiratory paralysis, urinary retention, fecal and urinary incontinence, loss of perineal sensation and sexual

function, persistent anesthesia, paresthesia, weakness, paralysis of lower extremities, loss of sphincter control, headache, backache, septic meningitis, meningismus, cranial nerve palsies; nausea, vomiting, chills, constriction of the pupils; allergic type reactions,

- Bupivacaine Hydrochloride and Epinephrine: see “Bupivacaine Hydrochloride” above; allergic-type reactions to sulfites in epinephrine-containing solutions
- Fentanyl citrate injection: respiratory depression, apnea, rigidity, bradycardia, respiratory arrest, circulatory depression or cardiac arrest, hypertension, hypotension, dizziness, blurred vision, nausea, emesis, diaphoresis, pruritus, urticarial, laryngospasm, anaphylaxis
- Morphine sulfate injection (Duramorph): pruritus, nausea, vomiting, constipation, urinary retention, headache, dizziness, euphoria, anxiety, hypotension, confusion, reduced male potency, decreased libido in men and women, menstrual irregularities including amenorrhea, depression of cough reflex, interference with thermal regulation, oliguria, urticarial, wheals, local tissue irritation, respiratory depression and/or respiratory arrest, tolerance, myoclonus, convulsions, dysphoric reactions, toxic psychoses, drug abuse and dependence; overdosage: respiratory depression with or without concomitant CNS depression, apnea, circulatory collapse, cardiac arrest

○ Describe how anticipated risks will be minimized:

- The patients will be monitored extensively during anesthesia administration and afterwards according to anesthesia protocols and will be attached to a continuous monitor and have blood pressure and pulse taken according to operating room protocol for regional anesthesia. The subjects will be monitored for local anesthetic toxicity according to routine anesthesia protocols (monitoring patients for symptoms and vital signs). During injection extreme care and caution will be used to ensure that the injection is not intravascular by aspiration prior to injection. Appropriate interventions for any perceived risk will take place. This will be performed in the operating room where all resuscitative equipment and personnel (including anesthesia physicians) are present.
- Document how potential benefits to participants or others justify potential risks

- Benefits of potential decreased postoperative pain above current baseline postoperative pain justifies potential risks
- Describe the plan for data storage and for maintenance of subjects' confidentiality
 - All records will be kept in a secure manner on a secure server (Box.com). Access to the records will only be by the listed protocol investigators and key personnel and the computer records will be password protected. All patients will be assigned a number and all information will be recorded under this number - not patient identifying information - and a separate list will be kept in a separate location under password protection listing medical records of patients identified to the code and only researcher [name] will have access to this list
 - Subjects will not be video or audio taped
- Data Analysis
 - Appropriate statistical methods will be used to evaluate study objectives
 - Hypothesis: The addition of incisional subcutaneous bupivacaine with epinephrine to standard spinal anesthesia regimen at the time of elective cesarean delivery will decrease postoperative narcotic usage by at least 25% in the first 24 hours
 - A statement regarding specifically what data are to be used to test the hypothesis (or to generate the hypotheses)
 - Our hypothesis will be tested by assessing cumulative postoperative opioid usage in the first 24 hours postoperatively
 - The statistical method(s) to be used to test the hypothesis with that data
 - Depending on the distribution of the data appropriate statistical analysis including one way ANOVA or non-parametric Kruskal Wallis test will be used to analyze the data. Categorical variables such as adverse events, we will be analyzed using Chi-Square analysis. Additionally, we will be using a linear mixed effects regression analysis to model the difference in mean pain scores during the hospital stay.
 - A power analysis to determine the sample size
 - See above for sample size calculation in Methods section) for power analysis
 - Describe methods for interim analyses or early stopping, if applicable
 - Data Safety Monitoring Board (DSMB) will review interim findings at the midpoint of the study. The study will be terminated early if

evidence of effect is established, if the intervention appears futile, or if harm is established. Specifically, if the p-value of the intervention-by-time effects based on data accumulated by the midpoint of the study is smaller than 0.005 (O'Brien-Fleming boundary), we will declare the superiority of the intervention. On the other hand, if the upper bound of the 95% confidence interval for the difference between the groups is less than 5%, we will declare futility of the intervention. The DSMB will also be authorized to recommend early termination for other reasons related to patient safety. We will have a planned interim analysis halfway through patient recruitment to stop the study if there is a significant impact

- Describe how possible confounding and/or effect modification will be addressed
 - All patients will be randomized and blinded to their intervention groups. Baseline demographic variables will be collected to assess for differences among the groups. Patients with a history of chronic pain syndromes or chronic opioid use will be excluded from the study.
- Describe how loss to follow up will be addressed
 - We will increase the power calculated sample size by 10% to account for loss to follow up

Data safety monitoring plan: Patient outcomes will be monitored in real time for side effects and patient safety. In order to maintain additional patient safety, a DSMP will be in place for the study. The data will be reviewed by two clinicians familiar with spinal anesthesia, cesarean birth and perioperative and postoperative management and complications, namely [name] (Obstetric Anesthesia attending) and [name] (Maternal Fetal Medicine attending). In addition, clinical researcher [name], will review the data. The Data safety monitoring committee will meet every 6 months. Minutes of the meetings including attendance, a summary of discussion and any relevant findings will be recorded. Data will be reviewed for adverse events throughout the study duration. The results of findings and recommendations of the team will be reported to the Albert Einstein College of Medicine institutional review board for review and action.

Data quality control and database management.

- Describe methods for data entry and data management
 - All data will be gathered by key personnel member [name] and entered into a password protected excel spreadsheet located on a secure Montefiore server (Box.com)
- Describe the mechanism for checking and editing the data.
 - Data will be checked monthly by randomly selecting patients to check all data input by a different key personnel member than originally entered the data
- Describe computer data security and subject confidentiality

- All records will be kept in a secure manner on a secure server (Box.com) on a secure excel spreadsheet with password protection; access to the records will only be by the listed protocol investigators and the computer records will be password protected; all patients will be assigned a number and all information will be recorded under this number - not patient identifying information - and a separate list will be kept in a separate location under password protection listing medical records of patients identified to the code and only researcher [name] will have access to this list
- Data given to researchers for future research projects:

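### The allergy exclusions omit sulfites, the one hazard the protocol lists for the Group 2 solution beyond plain bupivacaine

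*Combined protocol and SAP*

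**What the plan says.** Under Groups, Group 2 receives 20 ml of subcutaneous bupivacaine 0.25% with epinephrine. Group 1 receives plain bupivacaine and Group 3 saline. The background section describes no local infiltration as current standard care.

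The adverse-reaction list under Risks/Benefits covers the epinephrine solution by referring back to plain bupivacaine and adding a single item, "allergic-type reactions to sulfites in epinephrine-containing solutions". The same section says of the injection itself: "Risks of injection process include: pain, redness, infection or allergy to medication components".

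The Exclusion criteria contain two allergy items: "Known maternal allergy to bupivacaine or derivative" and "Known maternal allergy to oxycodone, ibuprofen, acetaminophen or derivative". Under Informed consent, the protocol says "These patients will be approached based on the inclusion/exclusion criteria noted above". Under Participant recruitment it adds "We are requesting a waiver of informed consent and HIPAA authorization to access medical records for recruitment purposes".

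Under Blinding, the envelope stays sealed until immediately before the cesarean. Only the anesthesia physicians, who prepare the syringe, then know the group.

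**The concern.** The protocol names a hazard specific to one arm's injection but does not exclude women known to be susceptible to it. Neither allergy item reaches sulfites, which the protocol ties to the epinephrine solution and not to bupivacaine. Screening that follows the written list would admit a woman with a known sulfite allergy. Her protection would then depend on a check that the protocol does not require.

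Two things are at stake. The first is an avoidable exposure to an injection that only the trial adds. The second is timing: if the allergy is noticed only once the envelope is open, the resulting deviation or withdrawal can occur only in Group 2, which is the arm named in the study hypothesis.

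**Working it through.** The plan gives no figure on this point to reproduce. The check compares the listed hazards with the eligibility text and then does some simple arithmetic.

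**Text comparison**

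| Hazard or component | Where the protocol lists it | Matching exclusion |
|---|---|---|
| Bupivacaine (spinal in all arms; injection in Groups 1 and 2) | Risks/Benefits, adverse reactions | Yes: "Known maternal allergy to bupivacaine or derivative" |
| Oral analgesics (all arms) | Risks/Benefits, adverse reactions | Yes: "Known maternal allergy to oxycodone, ibuprofen, acetaminophen or derivative" |
| Sulfites in the epinephrine solution (Group 2) | Risks/Benefits, adverse reactions | None |

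None of the remaining exclusions would catch a known sulfite allergy, and sulfites are mentioned nowhere else in the protocol. The measures for minimizing risk are monitoring, aspiration before injection, and resuscitation equipment and staff in the operating room. They limit intravascular injection and respond to a reaction, but none asks about allergy beforehand.

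**Who could catch it**

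- The recruiter may see the allergy in the records, but is directed only to the written criteria.
- The obstetric physicians who inject are not told what the syringe contains, so they cannot match it to the patient's allergies.
- The anesthesia physicians know the contents, but only after the envelope is opened.

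**Chance of assignment**

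Input from Power analysis: "276 subjects total- or 92 patients per group".

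P(Group 2, given an affected woman is enrolled) = 92/276 = 0.333, or 1/3.

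This is the chance of assignment. The chance of exposure can only be lower, because staff may intervene.

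**Effect on the sample size**

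Input from Power analysis: "this will require 255 subjects total (85 subjects per group".

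- Spare places in Group 2: 92 − 85 = 7.
- One withdrawal after the envelope is opened: 1/92 = 1.1% of the arm, leaving 91.
- Seven losses from all causes leave 92 − 7 = 85, and eight leave 92 − 8 = 84. Group 2 therefore falls below 85 only with eight or more losses.

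These figures assume that an intercepted woman is withdrawn. The protocol states no such rule, and she could instead go uninjected and stay in follow-up. In either case the effect on power is not material.

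**The case against.** The strongest reply is that this is a drafting preference. The list is headed as adverse reactions according to the FDA, not as contraindications, and nothing says each listed reaction needs its own exclusion. That is fair: making this an exclusion is a judgment, not the correction of a contradiction.

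The two existing allergy exclusions also concern drugs used in every arm, since bupivacaine is in everyone's spinal and the oral regimen is common to all. An exclusion for a component of one arm's solution would go a step beyond that pattern. This weakens the argument from consistency. It does not remove the reason to screen, because the protocol itself names component allergy as a risk of the injection.

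The protocol does not specify the product or its excipients, so the sulfite content of the syringe is inferred from the reaction list. That inference is reasonable, because the list is given for the study medications.

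Finally, harm requires a known allergy to be missed by the recruiter, the patient and the anesthesia physicians, and the consent form was not available for review. This limits how often the problem could arise. It does not supply a required check, and a catch by the anesthesia physicians once they know the group would come after assignment.

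**Conclusion.** The point holds as a minor participant-safety gap in one arm. A woman with a known sulfite allergy meets the written criteria and, if enrolled, has a 1/3 chance of assignment to the epinephrine solution. No expected number of affected women is claimed, because the documents give no prevalence. Power, error rates and the primary comparison are not materially affected.

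The conclusion rests on two things: that the Group 2 solution contains sulfites, as the protocol's own list implies, and that no sulfite check is made in the consent form or in local practice outside the protocol. If such a check exists, the gap is one of documentation only.

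**What to change.** Add one line to the Exclusion criteria: known maternal allergy to sulfites or to any other component of the study injection, including epinephrine. The protocol's list supports sulfites specifically. The wider wording follows from its general statement about component allergy.

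Apply the criterion at screening, before a study number and envelope are assigned, and to all three arms alike, so that eligibility does not depend on the assignment and no late catches fall on Group 2 alone.

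The cost is one line of text, one item on any screening checklist, and the loss of women with such a known allergy. Their number is not given and is assumed to be very small. They are replaced before enrolment, so the target of 276 and the analysis stay as they are.

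### The midpoint superiority rule tests a quantity other than the 24-hour opioid total, and no significance level is given for the final primary test

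*Combined protocol and SAP*

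**What the plan says.** Under interim analyses in the Data Analysis section, one efficacy look is planned at the midpoint. The quantity tested and its threshold are given by "if the p-value of the intervention-by-time effects based on data accumulated by the midpoint of the study is smaller than 0.005 (O'Brien-Fleming boundary". The consequence is that if this p-value "is smaller than 0.005 (O'Brien-Fleming boundary), we will declare the superiority of the intervention". The same paragraph ends with a general statement: "We will have a planned interim analysis halfway through patient recruitment to stop the study if there is a significant impact". That sentence names neither an outcome nor a level.

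The same section says the hypothesis will be tested on cumulative opioid use in the first 24 hours, which matches the primary outcome in the Methods. For the method it says that, depending on distribution, "appropriate statistical analysis including one way ANOVA or non-parametric Kruskal Wallis test will be used to analyze the data". No significance level is attached to that test.

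The only other level is in the Power analysis section, where the sample size was set "assuming a power of 80%, p value of 0.05 to detect a 25% difference in the primary outcome". It carries no adjustment for the interim look. The plan contains no alpha-spending statement, no final critical value and no statement of overall type I error.

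**The concern.** An interim look that can end the trial with a claim of superiority uses part of the type I error. The O'Brien-Fleming label suggests the authors meant to control this, but the plan gives only the first half of the boundary. The second half, about 0.048 at the end, is absent, and the one level tied to the primary outcome is 0.05.

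The pairing of 0.005 with 0.048 also holds 5% only if both looks use the same statistic on accumulating data. A 24-hour total is one number per patient and has no intervention-by-time effect. The interim test must therefore concern some repeated measure, and the plan does not say which. It could be cumulative opioid use at 4 to 48 hours, a secondary outcome that overlaps the primary, or the pain scores intended for the mixed model.

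At stake are an early claim of superiority that does not rest on the primary outcome, and a final p-value between about 0.045 and 0.05 with no pre-specified interpretation.

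**Working it through.** **Inputs from the documents.** Interim level 0.005, one look at the midpoint (Data Analysis). Design level 0.05, power 80%, SD 25, prior mean 47 mg, 25% difference, 85 per group in three groups (Power analysis). Final test: one-way ANOVA or Kruskal-Wallis (Data Analysis).

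**Assumptions.** Two-sided testing, one global test per look, no binding futility rule, information fraction 0.5. The correlation between the two statistics is not in the documents, so a range is shown.

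**1. Reproducing the plan's sample size.** The target difference is 0.25 × 47 = 11.75 mg, about 12. Take a three-group ANOVA with two groups differing by δ and the third midway. The noncentrality is λ = nδ²/(2σ²).
- δ = 12: λ = 85 × 144 / 1250 = 9.79. Power at 0.05 is 80.2%, and 85 is the smallest n per group that reaches 80%.
- δ = 11.75: λ = 85 × 138.06 / 1250 = 9.39. Power is 78.4%, and 89 per group would be needed.

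The plan's 85 per group is therefore reproduced with 12 mg and the full 0.05, which confirms that nothing was set aside for the interim look.

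**2. Overall type I error.** The probability of rejecting at either look is 1 − P(|Z₁| < c₁, |Z₂| < c₂), where c₁ = 2.807 corresponds to 0.005 and c₂ to the final level. With the same statistic at both looks, the correlation is √0.5 = 0.707. If the statistics are unrelated, the expression reduces to 1 − (1 − 0.005)(1 − final level). For example, 1 − 0.995 × 0.95 = 0.05475 and 1 − 0.995 × 0.952 = 0.05276.

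| Correlation | Final level 0.05 | Final level 0.048 | Final level 0.045 |
|---|---|---|---|
| 0.707 (same statistic) | 5.19% | 4.99% | 4.70% |
| 0.5 (assumed) | 5.34% | 5.14% | 4.85% |
| 0.3 (assumed) | 5.43% | 5.23% | 4.93% |
| 0 (unrelated) | 5.48% | 5.28% | 4.98% |

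Whatever the dependence, the sum of the two levels is a ceiling: 0.005 + 0.05 = 5.5%, 0.005 + 0.048 = 5.3%, 0.005 + 0.045 = 5.0%.

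**3. The three-group test.** The planned test has 2 numerator degrees of freedom. A simulation with 2-df chi-square statistics at both looks gives 5.20% with a final level of 0.05 and 5.01% with 0.048. The levels therefore carry over from the single-comparison calculation.

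**4. The level that restores 5%.** With 0.005 at the midpoint, the final level that gives exactly 5% is 0.0481 for the same statistic and 0.0452 for unrelated ones. The classical two-look O'Brien-Fleming pair is 0.0052 and 0.0480.

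**5. Power cost** (ANOVA, 85 per group, SD 25).

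| δ | 0.05 | 0.048 | 0.045 |
|---|---|---|---|
| 12 mg | 80.2% | 79.7% | 78.9% |
| 11.75 mg | 78.4% | 77.9% | 77.0% |

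**The case against.** The strongest reply is that the plan never says the final test will use 0.05. That figure is a sample-size input. By naming O'Brien-Fleming, the plan can be read as implying 0.048 at the end, and with one statistic at both looks the overall error is then 4.99%. This reply stands against a stronger reading that a reader might infer, namely that the trial's error rate is 5.2% to 5.5% and that a promised 5% is broken. The documents support neither part: they give no final level and state no overall error rate. The inflation is conditional on a choice the plan leaves open.

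The reply does not settle the matter. The implied 0.048 is written nowhere. Even if it were, the protection assumes one statistic at both looks, and the interim rule as written uses a different one.

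Four further points are fair. The lower correlations are assumptions; an interim model of cumulative opioid use could correlate well with the 24-hour total. A binding futility rule could lower the error, but the scale of its 5% margin is undefined, so it cannot be modelled. The normal cutoff 1.977 that goes with 0.048 applies to a single comparison, not to a three-group ANOVA or Kruskal-Wallis test; the level carries over and the cutoff does not. Finally, the numerical effect is at most half a percentage point.

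**Conclusion.** The concern holds in a limited form. As written, the interim rule can declare superiority on a quantity other than the primary outcome, and the plan gives no final significance level. These are gaps in the text and do not depend on any assumption about correlation. The outcome mismatch is the more consequential of the two.

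The error-rate effect is small and conditional: an excess of 0.2 to 0.5 percentage points if the final test uses 0.05, and from none to about 0.3 points if it uses 0.048. It would change a conclusion only for a final p-value between about 0.045 and 0.05. These figures rest on the assumptions listed with the calculation. If the final claim came instead from three unadjusted pairwise tests, the overall error would be about 12.7%, of which about 12.2% would arise without any interim look. That is a separate multiplicity question.

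**What to change.** In the interim paragraph of the Data Analysis section, replace the intervention-by-time test with the same three-group test of cumulative 24-hour opioid use that the final analysis will use. Keep p<0.005 at the midpoint, and state that the final primary test is significant at p<0.048. Express the rule as a p-value threshold, so that it applies to either ANOVA or Kruskal-Wallis. State sidedness, the overall 5% level, and whether the futility rule is binding.

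If a different interim outcome is kept, name it and use 0.045 at the end, which holds 5% under any correlation. That protects the error rate only; an early claim would still not rest on the primary outcome.

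The change is one or two sentences and should be made before interim data are seen. At 85 per group with SD 25 and 12 mg, power falls by 0.5 points at 0.048 and 1.3 points at 0.045. Restoring 80% would take 86 per group (258 evaluable) or 88 per group (264), against 255 now. Planned enrolment of 276 covers both, but the margin for missing data falls from 276 − 255 = 21 patients to 18 or 12.
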